5.2. Exclusion Criteria

Participants are excluded from the study if any of the following criteria apply.

Medical Conditions and History

- 1. Need for immediate effective anti-TB treatment as judged by the investigator.
- 2. Tested positive for COronaVIrus Disease-19 (COVID-19)/SARS-CoV-2 during the Screening Period with a PCR-based assay.
- 3. Evidence and/or history of extra-thoracic TB (e.g. miliary TB, abdominal TB, urogenital TB, osteoarthritic TB, TB meningitis, ocular TB), as judged by the investigator.
- 4. Evidence and/or history in the last 5 years of one or any combination of the following:
 - a. uveitis;
 - b. color vision deficiency;
 - c. amblyopia;
 - d. visual acuity worse than 20/25 after correction in either eye;
 - e. any known eye disease or prior eye surgery;
 - f. any systemic condition with ocular manifestations (i.e. Marfan, syphilis, diabetes, Beçhet, Vogt-Koyanagi-Harada, Lyme, or chronic inflammatory condition such as sarcoidosis, rheumatoid arthritis, psoriatic arthritis)

5. Evidence and/or history in the last 5 years of clinically significant medical condition(s) as judged by the investigator, including malignancies and unstable or uncontrolled hypertension.
6. Any current medical, psychiatric, occupational, or substance abuse problems that, in the opinion of the investigator, will make it unlikely that the participant will comply with the protocol.
7. For HIV infected participants:
 - a. CD4+ count <350 cells/ μ L, OR
 - b. AIDS-defining opportunistic infection or malignancies (except pulmonary TB).
8. Seated systolic/diastolic blood pressure assessed as vital sign (i.e. not from ECG) is less than 95/40 mmHg or greater than 145/95 mmHg at screening. Out-of-range blood pressure may be repeated twice with at least 5 minutes intervening.
9. Seated heart rate assessed as vital sign (i.e. not from ECG) is lower than 40 beats per minute (bpm) or higher than 110 bpm at screening. Out-of-range heart rate may be repeated twice with at least 5 minutes intervening.
10. A clinically significant ECG abnormality at screening. NOTE: The following can be considered not clinically significant:
 - a. mild first-degree atrio-ventricular block (P-R interval <0.23 sec);
 - b. right or left axis deviation;
 - c. incomplete right bundle branch block;
 - d. isolated left anterior fascicular block (left anterior hemiblock) in young athletic subjects.

Prior/Concomitant Therapy

See Section 10.6 (Appendix 6) for a list of commonly used prohibited medications (based on exclusion criteria # 11 to # 16). Please note that the list is not comprehensive and other medications with the features described below are also prohibited.

11. Use of medications active against Mtb within 3 months prior to the first dose of study drug.
12. Use of systemic immunosuppressive medications within 14 days prior to the first dose of study drug.
13. Use of strong inhibitors or strong inducers of cytochrome P450 (CYP) enzymes within 14 days prior to the first dose of study drug.
14. Use of inhibitors of phosphodiesterase (PDE) enzymes within 14 days prior to the first dose of study drug.
15. Use of medications known to affect the eye within 3 months prior to the first dose of study drug.
16. For HIV+ patients, use of medications listed in Section 10.6 (Appendix 6) within 3 months prior to the first dose of study drug.

Prior/Concurrent Clinical Study Experience

17. Participation in other clinical study(-ies) with investigational agent(s) within 6 months prior to trial start.

Diagnostic Assessments

18. The following laboratory values from blood collected during the Screening Phase, which represent Grade 2 or higher abnormalities per DAIDS Toxicity Table Version 2.1 (see Section 10.4, Appendix 4), will be cause for exclusion:
 - AST, ALT, alkaline phosphatase (ALP) \geq 2.5x upper limit of normal (ULN)

- Total bilirubin \geq 1.6x ULN
- Creatinine \geq 1.3x ULN
- Hemoglobin < 10 g/dL (male) or 9.5 g/dL (female)
- White Blood Cell Count (WBC) < 2,000 / mm³
- Platelets \leq 100,000 /mm³
- INR \geq 1.5x ULN
- PTT \geq 1.66 ULN
- PT \geq 1.25x ULN

ULN= upper limit of normal for local laboratory values

Grade 2 or higher abnormalities in other laboratory parameters from blood or urine Grade 1 abnormalities, or abnormalities from laboratory parameters not included in the DAIDS Toxicity Table Version 2.1, may lead to exclusion if the investigator considers them clinically significant.

Other Exclusion Criteria

19. History of allergy or hypersensitivity to any of the study drugs or related substances.
20. Positive urine drug screening for cocaine AND/OR amphetamines AND/OR opiates AND/OR methamphetamines. Note: screening will also be conducted for cannabinoids and results documented in the CRF; however, a positive test for cannabinoids is not an exclusion criterion.
21. Female participants currently pregnant or lactating/nursing; OR having positive serum pregnancy test during the Screening Phase OR planning a pregnancy within the 1 month after first dose of study drug. Refer to Section 10.3 (Appendix 3) for more information.

5.3. Lifestyle Considerations

Avoidance of pregnancy during the study: see Section 5.1.

5.4. Screen Failures

Screen failures are defined as participants who consent to participate in the clinical study but are not subsequently randomly assigned to study intervention/entered in the study. A minimal set of screen failure information is required to ensure transparent reporting of screen failure participants to meet the Consolidated Standards of Reporting Trials (CONSORT) publishing requirements and to respond to queries from regulatory authorities. Minimal information includes demography, screen failure details (i.e. why eligibility criteria were not met) and any SAE.

Rescreening is not permitted, except in special circumstances. The investigator may review rescreening eligibility, on a case-by-case basis, with the Sponsor.

6. Study Interventions

Study intervention is defined as any investigational intervention(s), marketed product(s), placebo, or medical device(s) intended to be administered to a study participant according to the study protocol.

6.1. Study Interventions Administered

Two interventions will be used in this study: participants will receive either TBA-7371 oral suspension or HRZE, a fixed dose combination of isoniazid [H], rifampicin [R], pyrazinamide [Z] and ethambutol [E]) oral tablets, commercially available in South Africa (Rifafour® e-275).¹

6.1.1. Composition

6.1.1.1 TBA-7371 Oral Suspension

The drug product is an extemporaneously compounded oral suspension.

The quantitative composition, function and quality of each ingredient in the drug product (TBA-7371 Oral Suspension, 25 mg/mL) is provided in Table 7 below.

Table 7. Composition of the TBA-7371 Oral Suspension, 25 mg/mL

Ingredient	Function	Quality Standard	Quantity per dose (100 mg)	Quantity per dose (200 mg)	Quantity per dose (400 mg)
TBA-7371 hydrochloride* equivalent to TBA-7371	Drug substance	In-house	100 mg	200 mg	400 mg
Purified water	Diluent	Commercially available	0.8 mL	1.6 mL	3.2 mL
Ora-Blend® **	Flavored oral suspending vehicle	Commercially available	Quantity required to 4 mL	Quantity required to 8 mL	Quantity required to 16 mL
Total volume			4 mL	8 mL	16 mL

*TBA-7371 hydrochloride salt is calculated using the assay value of free base from the certificate of analysis.

Quantity of HCl salt (g) = amount of free base equivalent divided by % assay value as free base.

** Purified water, sucrose, glycerin, sorbitol, flavoring, micro-crystalline cellulose, carboxymethylcellulose sodium, xanthan gum, carrageenan, calcium sulfate, trisodium phosphate, citric acid and sodium phosphate as buffers, dimethicone antifoam emulsion. Preserved with methylparaben and potassium sorbate.

6.1.1.2 HRZE Tablets

HRZE is a commercially available fixed dose combination of 4 TB drugs: isoniazid (H, 75 mg), rifampicin (R, 150 mg), pyrazinamide (Z, 400 mg), and ethambutol (E, 275 mg)

Rifafour® e-275 (Sanofi) tablets, a commercial presentation of HRZE approved and available in South Africa, will be used in this study.

See package insert ¹ (also enclosed in the study specific manual) for information on the composition of Rifafour® e-275 tablets.

6.1.2. Intervention Cohorts

During the Screening Phase participants will not receive TB treatment.

Participants who meet all inclusion and none of the exclusion criteria at the end of the Screening Phase will be enrolled sequentially in one of 5 cohorts in 3 escalation steps and randomized as follows.

- Cohort I: randomized to TBA-7371 oral suspension 100 mg QD OR HRZE tablets (Rifafour® e-275) QD for 14 days.
- Cohort II and Cohort III: randomized first to Cohort II OR Cohort III, and subsequently
 - Cohort II: randomized to TBA-7371 oral suspension 100 mg BID OR HRZE tablets (Rifafour® e-275) QD for 14 days.
 - Cohort III: randomized to TBA-7371 oral suspension 200 mg QD OR HRZE tablets (Rifafour® e-275) QD for 14 days.
- Cohort IV: randomized to TBA-7371 oral suspension 100 mg TID OR HRZE tablets (Rifafour® e-275) QD for 14 days.
- Cohort V: randomized to TBA-7371 oral suspension 400 mg QD OR HRZE tablets (Rifafour® e-275) QD for 14 days.

On Day 15 all participants will switch to standard of care TB treatment as determined by the National Health System.

6.1.3. Administration

Study drugs will be prepared and administered in an unmasked (unblinded) fashion based on the randomization list by authorized and trained site staff members.

All doses of study drug will be taken under direct observation of a study staff member.

TBA-7371 oral suspension will be administered every day from study Day 1 to Day 14 once (Cohorts I, II and V), twice (Cohort II) or three times (Cohort III) daily (see Section 6.1.2).

HRZE tablets (Rifafour® e-275) will be administered every day from study Day 1 to Day 14 QD as per Package Insert ¹ as follows:

- 40-54 kg: 3 tablets
- 55-70 kg: 4 tablets
- 71 kg and over: 5 tablets.

If a patient's weight changes between specified weight bands during the course of the Study Treatment period, the investigator will determine which of the measured weights to use for dosing.

The 1st dose of study drug will be administered at the same time each day for the individual participant. Subsequent doses will be administered as follows:

- BID schedules: 12 hours after 1st dose
- TID schedule: 7 hours and 14 hours after 1st dose.

Fasting must occur at least 2 hours before dosing and at least 1 hour after dosing.

When the dosing timing coincides with the time of other procedures, dosing will occur after completion of the procedures. It is important that dosing occurs at the assigned time. Procedures should be timed accordingly i.e. start before dosing time as appropriate.

6.2. Preparation/Handling/Storage/Accountability

6.2.1. Preparation

TBA-7371 will be prepared extemporaneously for 250 mL or 500 mL of a 25 mg/mL suspension. Please refer to the study specific manual(s) for preparation details.

Commercial HRZE tablets (Rifaxen® e-275) will be provided.

6.2.2. Handling

TBA-7371 oral suspension will be transferred and stored in Pyrex glass reagent bottles with a polypropylene screw cap without a liner. These bottles will be used for mixing, sampling and storage prior to administration. The required doses of the drug product will be dispensed using commercially available oral syringes of suitable capacity. The suspension will be dispensed just prior to dosing and not stored in the oral syringes.

6.2.3. Storage

Based upon the supportive stability study data, the recommended storage condition for batches of TBA-7371 oral suspension clinical trial material is 2-8°C (36-46°F). A do-not-use-beyond-date of 7 days after compounding has been assigned.

Rifaxen® e-275 tablets will be stored in a cool place, below 25°C as per Package Insert.¹

The study pharmacist (or designee) must confirm appropriate temperature conditions have been maintained during transit and during site storage for all study drugs received and that any discrepancies are reported and resolved before use. Upon receipt of study drug supplies, the study pharmacist (or designee) must immediately inspect supplies for damage. Any damage or discrepancy from the packing list must be documented and promptly discussed with the sponsor or CRO representative to determine the appropriate action.

6.2.4. Accountability

Only participants enrolled in the study may receive study drug and only authorized site staff may supply or administer study drug. All study drug must be stored in a secure, environmentally controlled, and monitored (manual or automated) area in accordance with the labeled storage conditions with access limited to the investigator and authorized site staff.

The principal investigator is responsible for study drug accountability, reconciliation, and record maintenance (i.e., receipt, reconciliation, and final disposition records).

Authorization for any unused study drug and supplies to be destroyed is the responsibility of the sponsor. Unused supplies will be destroyed according to the facility's SOPs or per local regulations. Any disposal of study drug conducted at the clinical site must be documented in the study file.

Further guidance and information for the preparation, handling, storage and accountability are provided in the study specific manual(s).

6.3. Measures to Minimize Bias: Randomization and Masking

6.3.1. Randomization

Participants will be enrolled in one of 5 cohorts in 3 sequential escalation steps as follows.

- Cohort I: TBA-7371 100 mg QD or HRZE (Rifafour® e-275) QD for 14 days.
- First escalation step (from Cohort I to Cohorts II and III). Participants will be randomized to Cohort II OR Cohort III.
 - Cohort II: TBA-7371 100 mg BID or HRZE (Rifafour® e-275) QD for 14 days.
 - Cohort III: TBA-7371 200 mg QD or HRZE (Rifafour® e-275) QD for 14 days.
- Second escalation step (from Cohort II and Cohort III to Cohort IV)
 - Cohort IV: TBA-7371 100 mg TID or HRZE (Rifafour® e-275) QD for 14 days.
- Third escalation step (from Cohort IV to Cohort V)
 - Cohort V: TBA-7371 400 mg 400 QD or HRZE (Rifafour® e-275) QD for 14 days.

Across Cohorts I, IV, and V, the design is non-randomized and open label, whereas the design is randomized with respect to Cohort II and III, which have the same total daily dose (200 mg). Within each cohort the design is randomized, active-controlled and open label. Within each cohort participants will be randomized unequally in a 5:1 ratio to TBA-7371 (N=15) or HRZE (N=3).

Participants will be randomized on Day -1 or Day 1 based on a randomly-generated sequence of participant identification (identifier) numbers (randomization schedule) using a validated Interactive Voice/Web Response System (IVRS/IWRS). Before the study is initiated, the telephone number and call-in directions for the IVRS and/or the log in information and instructions for the IWRS will be provided to the study sites.

6.3.2. Masking (Blinding)

This study will be open label for study participants, study site personnel, IDMC members, laboratory personnel involved in PK measurements and all sponsor and CRO personnel.

The study will instead be masked (blinded) for personnel involved in the conduct of all other laboratory procedures (including those for the primary endpoint).

6.3.3. Masking Break

Not applicable in this study.

6.4. Study Intervention Compliance

All doses of study drug will be taken under direct observation of a study staff member. Participant compliance with study intervention will be recorded on his/her eCRF.

6.5. Concomitant Therapy

No TB drug must be taken during the Screening Phase.

No TB drug other than study drugs (TBA-7371 and HRZE fixed dose combination) must be taken during the Study Treatment Phase (Days 1-14).

At the start of the Follow-up Phase (Day 15) participants will be switched to standard of care TB treatment.

All treatments listed in the exclusion criteria 11 to 15 are also not allowed throughout the Study Treatment Phase and Follow-up Phase (Days 1 through 42).

No vaccine should be administered during the trial.

Any allowed prescription medication, anti-inflammatory drug and antipyretic drug that the participant receives from enrollment through study Day 42 must be recorded along with reason for use, dates of administration including start and end dates and dosage information including dose and frequency.

The medical monitor may be contacted if there are any questions regarding concomitant or prior therapy.

6.6. Dose Modification

No dose modification of study drug is allowed.

6.7. Intervention after the End of the Study

There is no intervention planned after the end of the study.

7. Discontinuation of Study Drug and Participant Discontinuation/Withdrawal

7.1. Pausing and Resumption of Study Drug and Recruitment

If any one of the conditions listed below apply, an investigator and/or the sponsor will pause enrollment and study drug administration. If an investigator observes that a pausing rule is met, he/she will inform the sponsor as soon as possible and within 24 hours of the event. The sponsor will notify all investigators and IDMC of the pause in enrollment as soon as possible and within 24 hours of the event. The IDMC will then review all relevant safety data in an ad hoc meeting and recommend to the sponsor how to proceed. If the IDMC observes that a pausing rule is met, the IDMC will inform the sponsor ASAP and within 24 hours of the observation. The IDMC charter describes these processes in more detail.

If any of the below conditions are met, enrollment and administration of study drug will be paused:

- anaphylaxis with or without bronchospasm within 4 hours of study drug intake, indicative of an immediate hypersensitivity reaction;
- 3 or more of participants in the same or different cohorts experience adverse events with Grade 3 or higher intensity, considered related to study drug and similar to one another, as assessed by the investigator and/or the IDMC and/or the sponsor;
- an AE pattern of concern, as assessed by the investigator and/or the IDMC and/or the sponsor;

The decision to pause the study will be recorded in a memorandum to the study file and will trigger IDMC review.

IDMC recommendations will be recorded in a memorandum to the study file.

The IDMC may recommend resumption of study drug administration and enrollment with or without changes to the protocol.

The final decision to resume study activities or amend the protocol will be made by the sponsor.

The clinical site will be allowed to resume activities upon receipt of written notification from the sponsor.

Upon resumption of study drug administration, participants who will have missed up to 1 treatment day will continue in the study; participants who will have missed more than 1 treatment day will be withdrawn from the study and possibly replaced if the enrollment pause results in more than 2 early withdrawals (drop-outs) in a cohort.

7.2. Participant Discontinuation/Withdrawal from the Study

A participant will discontinue study treatment and end in-clinic hospitalization if the participant tests positive for COVID-19/SARS-CoV-2 anytime during the study treatment period, and will be referred for on-going TB treatment per national guidelines and for further evaluation for COVID-19. If the participant allows and the PI agrees, telephone follow-up may be completed in place of onsite visits on Day 28 and Day 42.

A participant may withdraw from the study at any time or may be withdrawn at any time at the discretion of the investigator for safety, behavioral, compliance, or administrative reasons. This is expected to be uncommon. The participant will be permanently discontinued both from the study intervention and from the study at that time.

See Section 10.1.5 (Appendix 1) regarding the participants' right to withdraw.

Participants who withdraw before Day 14 will be asked to complete the Early Withdrawal Visit assessments within 2 days of withdrawal (see Section 8.3.8).

Participants who complete the Study Treatment Phase, but do not return for the Day 28 visit will be asked to return for the Day 42 visit.

If a participant withdraws from the study, he/she may request destruction of any samples taken and not tested, and the investigator must document this in the site study records and the eCRF.

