Assess the impact on heart rate, blood pressure and ECG profile of each dose regimen of TBA-7371 and of HRZE over the 14-day treatment period.	
From Day 1 through Day 15:
 
 Mean and frequency distribution of changes in heart rate (HR), systolic blood pressure (SBP) and diastolic blood pressure (DBP) as measured by the following 2 (BP) or 3 (HR) methods: 
 manual (vital signs), after at least 10 minutes in supine position (“manual, supine”);

Objectives	Endpoints
	
 ▪ manual, after 2 (± 0.5) minutes in standing position (“manual, 2-min standing”); ▪ HR from ECG, supine position (“ECG, supine”) • Frequency of participants with $\ge 25\%$ increase in HR, decrease in SBP, decrease in DBP vs. baseline as measured with any of the methods described above. • Mean and frequency distribution of percentage of days with $\ge 25\%$ increase in HR, decrease in SBP, decrease in DBP vs. baseline. • Mean/median change from screening through Day 15 in PR, RR, QRS, QT, QTcF values from baseline ECG.
Assess whether there is tachyphylaxis over the 14-day treatment period for HR, SBP, DBP and eye symptoms.	
 • Mean change in HR, SBP and DBP from Day 1 to Days 4, 7, 10, 14 and 15 for each of the measurement methods described above. • Change in frequency of participants with eye symptoms (all, severe, serious) and change in mean visual acuity score and frequency of color vision abnormalities (tritan, protan, deutan) in one or both eyes and degree of severity (mild, moderate, and severe) from Day 1 to Days 4, 7, 10, 14 and 15.
Assess whether cardiovascular and/or ophthalmic AEs persist or recur up to 4 weeks after discontinuation of treatment with TBA-7371.	
 • Mean change in HR, SBP and DBP from screening to Days 28 and 42 and from Day 14 to Days 28 and 42 for each of the measurement methods described above. • Change in frequency of participants with eye symptoms (all, severe, serious) and change in mean visual acuity score and frequency of color vision abnormalities (tritan, protan, deutan) in one or both eyes and degree of severity (mild, moderate, and severe) from screening to Days 28 and 42 and from Days 1-15 (combined) to Days 28-42 (combined).

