8.3.3. Pregnancy Status Assessment

A serum beta human chorionic gonadotropin (β HCG) test will be performed during the Screening Phase to assess eligibility, on Day 15, (the day after the last dose of study drug) and on Day 42 (end of the Follow-up Phase). The test will also be conducted during the Early Withdrawal Visit if the participant withdraws from the study between Day 1 and 14.

Details on serum collection procedures and on the laboratory are provided in the study specific manual(s).

If a pregnancy is reported during the study, the investigator should inform the local medical monitor within 24 hours of learning of the pregnancy and should follow the procedures outlined in Section 10.3 (Appendix 3).

If a participant becomes pregnant during the study, she will be withdrawn from study drug and from all study procedures going forward. If the pregnancy is discovered during the Treatment Phase, the participant will undergo the Early Withdrawal Visit and thereafter be discharged from the hospital. However, she will be encouraged to undergo the Day 28 and Day 42 visits.

Investigators must make an effort to collect outcomes of pregnancies discovered during the study and communicate them to the sponsor and/or CRO.

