8.3.8. Early Withdrawal Visit

Participants who withdraw from the study before Day 14 will be asked to complete the Early Withdrawal Visit assessments within 2 days of withdrawal. These are as follows (see Table 4):

- Focused PE (see Section 0)
- Pregnancy status assessment (see Section 8.3.3)
- Clinical Safety laboratory assessments (see Section 8.3.4)
- Vital signs and body weight (see Section 8.3.5)
- ECG (see Section 0)
- Eye assessment (see Section 8.3.7)
- AE and SAE (see Section 0)
- Concomitant treatments (see Section 8.5).

Participants who complete the Study Treatment Phase, but do not return for the Day 28 visit will be asked to return for the Day 42 visit.

If a participant withdraws from the study, he/she may request destruction of any samples taken and not tested, and the investigator must document this in the site study records and the eCRF.

If a patient is withdrawn from the study due to a positive COVID-19/SARS-CoV-2 test and maintains consent, a telephone follow-up may be documented on Day 28 and Day 42.

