8.4.1. Time Period for Collecting AE Information

AE, SAE (including Serious ADR) and AESI will be collected from the time each participant has signed the ICF until he/she has completed the last follow-up visit (Day 42) or the EWV.

All SAE (including Serious ADR) and AESI will be reported to the sponsor or designee within 24 hours, as indicated in Section 10.2.5 (Appendix 2). The investigator will submit any updated SAE/AESI data to the sponsor or designee within 24 hours of it being available.

The investigator is not obligated to actively seek AE or SAE after conclusion of study participation. However, if the investigator learns of any SAE, including a death, at any time after a participant has been discharged from the study, and he/she considers the event to be related to the study intervention or study participation, the investigator must promptly notify the sponsor.

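### With two exceptions (COVID-19 and pregnancy), participants who stop study drug early leave the study, so the Day 28/42 persistence summaries rest mainly on people who completed 14 days

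*Protocol*

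**What the plan says.** The objective is in Protocol 1.1.4.2 (repeated in 3.2): "Assess whether cardiovascular and/or ophthalmic AEs persist or recur up to 4 weeks after discontinuation of treatment with TBA-7371". Its cardiovascular endpoint is "Mean change in HR, SBP and DBP from screening to Days 28 and 42 and from Day 14 to Days 28 and 42". The eye endpoints (symptoms, acuity, colour vision) use the same two visits.

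Protocol 7.2 provides that a participant "may be withdrawn at any time at the discretion of the investigator for safety, behavioral, compliance, or administrative reasons". It continues: "The participant will be permanently discontinued both from the study intervention and from the study at that time". Other routes off study drug have the same result. After a pause (7.1), "participants who will have missed more than 1 treatment day will be withdrawn from the study and possibly replaced". Under 8.5 and 8.6, a participant who needs a prohibited medication during treatment, or who has an overdose, is discontinued from the study.

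What remains is in 8.3.8: "Participants who withdraw from the study before Day 14 will be asked to complete the Early Withdrawal Visit assessments within 2 days of withdrawal". That visit includes vital signs, ECG and the eye assessment. Under 8.4.1, adverse events are collected from consent "until he/she has completed the last follow-up visit (Day 42) or the EWV".

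There are two exceptions. A participant who tests positive for COVID-19 during treatment may have telephone contact at Days 28 and 42 (7.2, 8.3.8). For a participant found to be pregnant, 8.3.3 says: "However, she will be encouraged to undergo the Day 28 and Day 42 visits".

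**The concern.** The objective concerns what happens after the drug is stopped. People taken off the drug because of a heart-rate, blood-pressure or eye event are among those who would inform it most, and no Day 28/42 measurements are planned for them. Protocol 2.3 reports that the frequency of these events was dose related in the first human study. Safety withdrawals could therefore cluster at the regimens for which the persistence answer matters most in choosing what to take forward. If so, the Day 28/42 tables would describe mainly people who tolerated 14 days and could look more reassuring than the experience of everyone treated.

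**Working it through.** Apart from one small illustration, the check sets the passages side by side.

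1. **Is there a general route to stop drug and stay in the study?** No. Withdrawal under 7.2, more than one missed day after a pause (7.1), prohibited medication (8.5) and overdose (8.6) all end study participation. The only departures are the COVID-19 and pregnancy provisions. A telephone call can capture symptoms and events, but not heart rate, blood pressure, ECG, acuity or colour vision.

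2. **Does event follow-up fill the gap?** In part. Section 8.4 makes the investigator responsible for following events that are serious, related, or the cause of discontinuation, with no grade limit. Section 10.2.6.1 follows all serious events and non-serious events of special interest until they resolve or stabilise. Under 10.2.5 the latter include Grade 2 or higher heart-rate, blood-pressure and eye events. What is left out is the scheduled testing at Days 28/42 and the detection of new or recurrent non-serious events after the EWV.

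3. **Does the SAP compensate?** No. By-time-point denominators count only participants assessed at that time point (SAP 12.2 to 12.4) or with values at both baseline and that time point (12.5.2, 12.6.2). Visits are used as recorded, without windows (9.8), so an EWV does not stand in for Day 28 or 42. No adjustment of these summaries for early withdrawal is described. SAP 10.1 does tabulate stopping treatment separately from stopping the study, although the Protocol mostly makes them one event.

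4. **How many could be missing?** Each cohort has 18 participants (15 TBA-7371, 3 HRZE), and the first two treatment-phase drop-outs are not replaced (Protocol 1.1.6). The stated minimum of completers reproduces: 18 − 2 = 16. Two unreplaced drop-outs are 2/18 = 11.1% of a cohort, or 2/15 = 13.3% of a TBA-7371 group if both were on TBA-7371. Third and later drop-outs are replaced, so this is not a cap on withdrawals. A replacement restores the number of completers but not the missing follow-up.

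5. **Illustration.** The documents give no withdrawal rate, so assume 0, 1 or 2 early stoppers in a group of 15, no replacement, and no completer with a persistent event:

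| Early stoppers | By-visit table shows | All 15 could be as high as |
|---|---|---|
| 0 | 0/15 | 0/15 = 0% |
| 1 | 0/14 | 1/15 = 6.7% |
| 2 | 0/13 | 2/15 = 13.3% |

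The right-hand column is an upper bound, reached only if every early stopper has a persistent event.

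**The case against.** The strongest reply is that these people are not abandoned. They have safety tests at the EWV. A visual change that led to withdrawal must be followed under 8.4 whatever its grade, and 10.2.6.2 requires further measurements where medically indicated. Such an event would appear in the adverse event listing with its outcome and resolution date (SAP 12.1) and could contribute to the eye-event duration summary (SAP 12.2). This stands. The case would be missing from the by-visit tables, not from the report.

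Several stronger readings are tempting but not supported:

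- **Every early stopper goes without Day 28/42 contact.** The COVID-19 and pregnancy provisions say otherwise.
- **Grade 1 events are not followed.** Section 8.4 covers them if they are related or caused discontinuation.
- **The tables would carry a misleading confidence interval.** The SAP plans only frequencies and proportions for the by-time-point eye, acuity and colour summaries. Its single-proportion code (Appendix 4) is mid-P, not Clopper-Pearson.
- **A pause would bias the results towards people who tolerate the drug.** A pause removes participants regardless of their own tolerability, and only those who missed more than one treatment day. Someone with at most one treatment day left cannot meet that condition. A pause costs numbers, but does not in itself select for tolerability.
- **The primary safety endpoint is materially affected.** It is analysed over the full Safety population (SAP 12.1.1), and anyone withdrawn for a severe or serious event is already counted. Only a first such event after the EWV, off study drug, could be lost. Related serious events learned of later must still be notified (8.4.1).

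The reply also limits the remedy. Someone who stops on Day 4 is 28 − 4 = 24 and 42 − 4 = 38 days off drug at the two visits, against 14 and 28 days for a completer. The second visit then falls outside the objective's four weeks, and there is no Day 14 value for the Day 14 contrast. This affects how such participants should be presented. It does not remove the case for seeing them.

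**Conclusion.** The point holds in a limited form. Outside the two exceptions, stopping study drug early, including for safety, ends scheduled assessment at the EWV and ends collection of new or recurrent non-serious events. The Day 28/42 persistence and recurrence summaries therefore rest mainly on people who completed 14 days and could understate persistence. Event-level follow-up reduces the loss but does not supply the endpoint measurements.

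The size cannot be determined. No withdrawal rate is stated, and 7.2 expects withdrawal to be rare. Per early stopper the possible effect is one participant in 15 (6.7 percentage points) in a TBA-7371 group. A downward bias requires that early stoppers have persistent or recurrent effects more often than completers. That is plausible for safety withdrawals but not shown: Protocol 2.3 describes the vision events of the first study as short-lived and resolving before the next dose.

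The change is still worth making, because it is cheap and serves a stated safety objective.

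**What to change.** - **Protocol 7.1, 7.2, 8.3.8 and 8.4.1:** separate discontinuation of study drug from withdrawal from the study. Ask participants who stop drug early without withdrawing consent to complete the EWV and then attend the existing Day 28 and Day 42 visits, by telephone where that is already allowed. Continue adverse event collection to Day 42. No rule on when treatment stops is altered.
- **SAP 12:** include these participants in the Day 28/42 change-from-baseline and frequency summaries, flagged, and also show them separately with days since last dose. Leave them out of the Day 14 to Day 28/42 contrast.
- **Reconcile the wording:** 8.4 (follow-up of events that caused discontinuation) with 8.4.1 (collection ending at the EWV); 7.2 with 8.3.8 on whether a COVID-19-positive participant only stops treatment or is withdrawn from the study; and 8.3.3, which removes a pregnant participant from all further procedures yet encourages both visits.

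The cost is amendment wording, a small SAP change and two already defined visits for what should be a few participants. Some will decline to return, so the gap will narrow but may not close.
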